### 5.3.8 Echocardiography or MUGA

An echocardiography or MUGA assessment will be performed at Screening, and after every 6 months (every 8 cycles thereafter i.e. Cycle 9, Day 1, Cycle 17, Day 1, Cycle 25, Day 1, Cycle 33 Day 1).

Clinically significant findings identified prior to start of dosing must be checked against the study exclusion criteria ([Section 3.2](#)).

Patients who discontinue BGB324, but continue with monotherapy pembrolizumab, will stop undergoing an echocardiogram or MUGA assessment. Their final echocardiogram / MUGA assessment will occur if their next scheduled assessment is within the next 6 weeks (of discontinuing BGB324).

### 5.3.9 Electrocardiogram

A resting 12-lead ECG will be performed at the times given Schedule of Study Assessment [Table 4](#) and [Table 5](#). Each assessment time point must be performed in triplicate.

All 12-lead ECGs should be recorded while the patient is in the supine position. ECGs will be recorded at 25 mm/sec. All efforts should be made to ensure that an identical ECG machine is used to collect traces for individual patients. The Investigator or designated physician will review the ECG results.

If any clinically significant findings are observed on the ECG, the Investigator will record it as part of the medical history prior to the start of dosing, and as an AE post dose where the finding represents a change from baseline. Clinically significant findings identified prior to start of dosing must be checked against the study exclusion criteria ([Section 3.2](#)). Note that the average value of the three assessments performed at each time point should be applied, except at Screening, where both the Screening and pre-dose Cycle 1 Day 1 assessments should be combined. Patients may be excluded based on the initial triplicate assessment at Screening.

Patients who discontinue BGB324, but continue with monotherapy pembrolizumab will stop undergoing an ECG.

Patients who have a BGB324 interruption of 14 days for toxicity (see [Table 12](#) and [Table 13](#)) will require an ECG twice weekly for the 2 weeks following recommencement of BGB324 daily dosing. This is to ensure cardiac safety monitoring whilst BGB324 returns to steady state.

### 5.3.10 Tumor imaging

Efficacy endpoints in this study, including ORR, DoR, PFS will all be based on tumor imaging evaluation by RECIST 1.1.

RECIST assessments will be performed at the times given in Schedule of Study Assessment Table 4 and Table 5 using contrast-enhanced CT (preferred method) or MRI assessments of chest, abdomen, and pelvis. X-ray scans can be used where appropriate. Bone scans and brain scans should be conducted in the 6 weeks prior to study entry. Subsequently, x-ray, bone scans and brain scans will be used as appropriate. Additional anatomy should be imaged based on signs and symptoms of individual patients at baseline and follow-up.

Baseline assessments should be performed no more than 28 days before start of study treatment (6 weeks for brain and bone scans), and ideally should be performed as close as possible to the start of study treatment. The Screening imaging assessments must confirm the patient has measurable disease per RECIST 1.1 (see [Section 3.1](#)).

For each patient, the same modality used at Screening must be used serially throughout the duration of study participation. All imaging procedures will be performed according to standard local imaging protocols to ensure consistency across study assessments.

All radiological and non-radiological (e.g. MRI) scans will be reviewed by the local site investigator; and if possible, stored electronically (de-identified with the patient's notes) at site.

A maximum of 5 target lesions (TLs) must be selected at baseline. All target lesions are measurable. Target lesions should be selected on the basis of their size (longest diameter for non-nodal lesions or short axis for nodal lesions), but in addition should be those that lend themselves to reproducible repeated measurements. All remaining lesions present at baseline are considered non-target, irrespective of whether they are measurable.

Disease assessments will be performed as per the schedule described in [Table 3](#), [Table 4](#) and [Table 5](#) – that is, every 9 weeks  $\pm 7$  days for the first 46 weeks relative to the date of first treatment administration and then every 12 weeks  $\pm 7$  days thereafter until confirmed objective disease progression as defined by RECIST 1.1 (irrespective of a delay to treatment, or the reason for stopping treatment or subsequent therapy).

Any other sites at which new disease is suspected should also be adequately imaged at a follow-up visit.

If an unscheduled assessment is performed and the patient has not progressed, every attempt should be made to perform the subsequent assessments at their scheduled visits.

In addition to performing further scans where clinically indicated, scans also should be performed, as appropriate, to confirm response or disease progression.

### **5.3.11 Disease assessment**

A disease assessment according to RECIST 1.1 will be performed and all measurements of existing target lesions and new or existing non target lesions will be recorded in the CRF whenever a tumor imaging assessment is made during the Treatment period, Post Treatment Visit or during Follow Up Visits.

For more information on data evaluation by RECIST 1.1 for studies with checkpoint inhibitors, please refer to [Section 8.5](#).

### **5.3.12 Biomarkers**

Evaluation of biomarkers will be performed at the time points described in Schedule of Study Assessment [Table 4](#) and [Table 5](#).

Blood samples will be collected at these time points to prepare PMBC and blood samples for assessment of Axl inhibition and other relevant markers including sAxl such as MAPK signaling pathway intermediates (ERK/pERK), pAxl expression and T-cell populations, Akt, pAkt, SLFN11, Bcl2, and Puma.

Patients who discontinue BGB324, but continue with pembrolizumab monotherapy are not required to provide further blood samples for biomarker evaluation.

Full details of the blood volumes required, plus requirements for sample collection, handling and shipment to the assigned central laboratory, will be described in Laboratory Manual for the study.

### **5.3.13 Tumor Sample Requirements**

All patients are required to provide a fresh (newly acquired) tumor biopsy at Screening. Tumor specimens are to be submitted in sufficient quantity to allow for PD-L1 IHC and Axl IHC analysis (see the Pathology Manual).

Samples with limited tumor content (<100 viable tumor cells), cytology, cell block, decalcified or formalin fixed but previously frozen, frozen sample, plastic embedded, bone, bone marrow, clot and fine needle aspirates are inadequate for defining tumor PD-L1 and Axl status.

Axl expression can only be obtained from a fresh (newly acquired) tumor tissue sample. PD-L1 expression can be determined from either a fresh (newly acquired) or archival sample. In all cases, the tumor tissue must not have been previously irradiated.

Different testing laboratories will be used for Axl kinase and PD-L1 expression.

The fresh (newly acquired) tumor tissue sample will be either newly obtained core needle biopsy (minimum gauge 18) or newly obtained excisional biopsy.

The following tumor tissue options are available (all options require fresh tumor tissue sample, however, if there's insufficient fresh tumor tissue available, the 3rd option below allows the submission of archival tissue in addition to the fresh tissue sample):

- Where only a core needle biopsy is used, a minimum of 4 core biopsy samples are required. These should be placed in formalin and processed into 2 single paraffin embedded (FFPE) blocks (2 cores in one block and 2 cores in the other block) within 24-48 hours.
- Alternatively, where only a newly obtained excisional biopsy sample is used, this biopsy should be processed into 2 paraffin embedded (FFPE) blocks within 24-48 hours.
- Alternatively, 2 core needle (fresh tumor) biopsies or a single newly obtained excisional biopsy sample can be submitted (processed into one FFPE block), together with either an archival (FFPE) tumor tissue block or a minimum of 10 unstained slides each 5 $\mu$ m cut from the archival tumor sample block. The unstained slides must arrive at the testing laboratory within 14 days. In this option, an archival FFPE block is strongly preferred over unstained slides.

Archival blocks must be clearly labelled as archival.

Slides cut from an archival tissue block must be clearly marked as having come from an archival block.

Finally, where patients also have (additional) archived biopsy material which is suitable for additional (such as exploratory) biomarker assessment a sample of this material (either as an archival FFPE block or slides cut (and paraffin dipped) from the archival block) can also be prepared for study biomarker assessment. The patient will be offered a separate optional patient consent to enable this 'archival biomarker tumor sample' to be submitted.

Optional 'on study' tumor tissue (fresh tissue) biopsies can be conducted on up to 2 separate occasions on suitable lesions (for example, lesions that have progressed). Separate patient consent is required for these 'on study' biopsies.

Full details of the requirements for both fresh and archival biopsy sample collection, handling and shipment to the assigned (central) laboratories, will be described in the Pathology and Laboratory Manuals for the study.

### 5.3.14 Pharmacokinetics

Blood samples will be collected for the evaluation of the levels of BGB324 and pembrolizumab in plasma at the time points described in Schedule of Study Assessment [Table 4](#) and [Table 5](#).

Nominal PK blood sampling times should be adhered to as closely as possible. It is essential that the actual time and date of collection of each blood sample be recorded in the patient's records and in the CRF.

Full details of sample collection and handling for these samples will be described in Laboratory Manual for the study.

Full details of the blood volumes required, plus requirements for sample collection, handling and shipment to the assigned central laboratory, will be described in Laboratory Manual for the study.

## 6 STUDY MEDICATION AND ADMINISTRATION

Investigational Medicinal Product (IMP) will be provided by the Sponsor as summarized in [Table 11](#). Both BGB324 and pembrolizumab will be labelled in compliance with GMP Annex 13 requirements or other applicable local regulatory guidelines.

**Table 11: Product Descriptions**

Product Name & Potency	Dosage Form
BGB324 100 mg	HPMC capsule
MK-3475 10 mL, 100 mg/vial (Liquid) (4 mL fill volume, 25 mg/mL potency)	Solution for Injection

### 6.1 Preparation and Dosing of Study Treatments

Further details on preparation and administration of both BGB324 and pembrolizumab are provided in the Pharmacy Manuals.

#### 6.1.1 BGB324

BGB324 is provided in bottles containing a specified number of capsules per bottle to dispense to the patients. **Patients will be asked to take the specified number of capsules for their prescribed dose on an empty stomach at a regular time each day with water.** On pembrolizumab dosing days, patients will be asked not to take their BGB324 dose before coming into the clinic. On these days, pembrolizumab will be administered first, and the patient observed for 1 hour after the end of infusion (for infusion and other AEs), prior to taking their BGB324 dose (on an empty stomach and with water). Patients should not eat for at least one hour after taking BGB324.

#### 6.1.2 Pembrolizumab

Pembrolizumab will be administered at a dose of 200 mg (two vials) given as a 30 minute i.v. infusion through an intravenous line containing a sterile, non-pyrogenic, low-protein-binding 0.2-5 micron in-line or add-on filter. Dosing will be on Day 1 of each 3-week treatment cycle.

Trial treatment of pembrolizumab may be administered up to 3 days before or after the scheduled Day 1 of each cycle due to administrative reasons.

Sites should make every effort to target infusion timing to be as close to 30 minutes as possible. However, given the variability of infusion pumps from site to site, a window between -5 minutes and +10 minutes is permitted i.e. infusion time may be 30 minutes -5 min/+10 min.

## 6.2 Treatment Compliance

The patient will be asked to bring all bottles, including the empty ones, with them to each study visit to check compliance and for the Drug Accountability to be completed in the eCRF.

At each visit the Investigator or study staff will question the patient about the proper intake.

Proper intake, missed doses or failures in compliance will be recorded in the patient's file. The patient will be instructed as to the importance of taking their BGB324 in accordance with instructions.

## 6.3 Storage of Study Treatments

### 6.3.1 BGB324

BGB324 will be shipped to the site and must be stored at the site in a secure location under controlled, ambient temperature conditions (<25 °C or <77 °F). Instructions for the storage of dispensed BGB324 at home will be provided to every patient enrolled in the clinical study.

### 6.3.2 Pembrolizumab

Pembrolizumab (in 10 mL glass vials) will be shipped to the site and must be stored as follows:

- Cold storage (2 to 8 °C; 36 to 46 °F);
- Protect from light (a maximum of 24 hours exposure to light is permitted);
- Do not freeze;
- Do not shake.

## 6.4 Drug Accountability

The Investigator shall take responsibility for and shall take all steps to maintain appropriate records and ensure appropriate supply, storage, handling, distribution and usage of trial treatments in accordance with the protocol and any applicable laws and regulations.

The Investigator may assign some or all of the Investigator's duties for drug accountability to an appropriate pharmacist. Roles and responsibilities of site staff will be recorded in the TMF.

The investigator is responsible for keeping accurate records of the clinical supplies received from the sponsor or designee, the amount dispensed to and returned by the patients and the amount remaining at the conclusion of the trial. For all trial sites, the local country sponsor personnel or designee will provide appropriate documentation that must be completed for drug accountability and return, or local discard and destruction, if appropriate. Where local discard and destruction is appropriate, the investigator is responsible for ensuring that a local discard/ destruction procedure is documented.

Certificates of delivery and return must be signed by the responsible pharmacist, and copies retained in the Pharmacy File.

The medication provided for this study is for use only as directed in the protocol. It is the Investigator and their institution's responsibility to establish a system for handling study drug to ensure that:

- deliveries of BGB324 and pembrolizumab are correctly received by a responsible person;
- such deliveries are recorded;
- study treatments are handled and stored safely and properly as stated on the label;
- study drug is only dispensed to study patients in accordance with the protocol; and
- any unused study drug is destroyed locally or returned for destruction in liaison with the study monitor.

## 6.5 Method of Enrolling Patient to Study Treatment

During Screening, patients will be allocated a unique patient number from the RAVE, once written informed consent has been obtained. Patients will continue to be identified by this number throughout the study. Once a Subject Number has been assigned, it cannot be used again.

## 6.6 Dose Modifications

**Note: Three toxicities have been identified as potentially overlapping with both BGB324 and pembrolizumab – diarrhea, rash and renal toxicity. Please see [Section 6.6.4](#) for the management of these toxicities.**

Other toxicities can be managed as described in [Section 6.6.1](#), [Section 6.6.2](#) and [Section 6.6.3](#).

### 6.6.1 BGB324 dose modification for toxicity

If a patient experiences drug related toxicity that requires treatment with BGB324 to be interrupted, a delay of up to 14 days is permitted to allow for resolution of toxicity. In the absence of recovery, treatment with BGB324 should be discontinued. See [Table 12](#).

If treatment with BGB324 is interrupted, the relevant toxicity must have resolved to  $\leq$ Grade 1 or tolerable Grade 2 or baseline for treatment to recommence.

Only one dose reduction from 200 mg to 100 mg daily dose is possible.

**Table 12: Dose Modification for BGB324-related Toxicity**

Grade (CTCAE)		Recommended Dose Modification
Grade 1 and Grade 2 (tolerable)		
Any occurrence		Maintain dose of 200 mg if toxicity is tolerated by the patient
Grade 2 (intolerable)		
1 st or 2 nd occurrence of same adverse event		Interrupt treatment until toxicity returns to baseline, Grade 1 or tolerable Grade 2 Resume dosing at 200 mg
3 rd occurrence of same adverse event		Interrupt treatment until toxicity returns to baseline, Grade 1 or tolerable Grade 2 Dose reduce to 100 mg
4th occurrence of same adverse event		Discontinue permanently
Grade 3		
1 st occurrence		Interrupt treatment until toxicity returns to baseline, Grade 1 or tolerable Grade 2 Dose reduce to 100 mg or Discontinue permanently if dose has already been reduced
2 nd occurrence of same adverse event at G3		Discontinue permanently
Grade 4		
1 st occurrence		Discontinue permanently
Notes:		

 
Treatment interruption for BGB324-related toxicity should be limited to 14 days
 
Dose reduction below 100 mg daily is not possible (a single capsule contains 100 mg BGB324)
 
Patients being considered for dose reduction or permanent discontinuation of BGB324, may be discussed with
 
		

Grade (CTCAE)	Recommended Dose Modification
the Medical Monitor	
• Patients require an ECG twice weekly for the first 2 weeks after recommencing BGB324 following an interruption (see Section 5.3.9 )	

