**Figure 2: BGB324 in combination with anti mCTLA4 and anti mPD-1**

### 1.3.2 Non-clinical toxicology of BGB324

To support clinical studies with BGB324 a series of animal toxicology and safety studies, including 28-day repeat dosing studies in rodents and monkeys and a single dose telemetered cardiovascular (CV) safety study in monkeys, have been conducted. Comparisons of the data reported in the rodent and monkey studies indicate that primates are more sensitive to BGB324 on a per body weight basis.

The results of the repeat dose 28-day study in monkeys identified the liver, reticuloendothelial system and hematopoietic system as target organs. These events were largely thought to be due to macrophage accumulation, and were only partially reversible across the planned 16-day recovery period, although this was anticipated to be due to the slow elimination of the compound. Similar findings were identified in mice treated across a range of dose levels with partial recovery noted 16 days later.

In the CV safety study, single oral administration of BGB324 (7.5 mg/kg – 60 mg/kg) was associated with recoverable, non-adverse decreases in heart rate and corresponding increases in the RR interval durations. Dose-dependent increase in QTc interval was noted at all dose levels; the magnitude of the QTc effect at the highest dose level was 17%, whilst at 7.5 mg/kg and 15 mg/kg, the change generally fell below 10% compared to vehicle control and pre-dose values. These observations were consistent with the previously identified IC50 for human ether-à-go-go related gene (hERG) channel inhibition of 0.53 µM BGB324.

In an academic model of osteoporosis, BGB324 was administered in combination with high dose corticosteroids (12.5 mg/kg per day of prednisolone). In this research study, 6 out of 7 mice experienced severe toxicity after five continuous days of combination therapy. Four of the 6 animals (that developed severe toxicity) died and the other 2 were euthanized for humane reasons. The exact mechanism of this effect is currently under investigation. The mice received very high levels of corticosteroids to induce rapid onset of osteoporosis – on a mg/kg basis, the corticosteroid dose was 20 fold higher than a typical high dose commonly used in clinical practice. Additionally, the dose of BGB324 used in this model was 50mg/kg which is 6 fold higher than the maximum exposure observed in human clinical studies.

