### 6.6.2 BGB324 dose modification for QTc

Treatment with BGB324 produces QTc prolongation. In order to reduce the risk of QTc prolongation, all efforts should be made to maintain the patient's serum potassium levels at  $>4$  mmol/L during treatment with BGB324 and for 2 weeks following completion of therapy (at an unscheduled visit, if required). Serum calcium and magnesium should be measured and reasonable efforts made to maintain at normal levels throughout treatment. Patients with an average QTc of  $\geq 480$  ms should be closely monitored until the QTc falls below 480 ms; electrolytes should be measured and corrected as necessary.

If a patient experiences QTc prolongation, BGB324 dosing should be reduced as outlined in [Table 13](#). **Treatment with BGB324 should be permanently discontinued in the presence of ventricular arrhythmia.**

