**Table 13: Dose modification of BGB324 for QTc Prolongation**

QTcF	Recommended BGB324 Dose Modification
Grade 1 (450-480 ms)	
Any occurrence	No dose modification required
Grade 2 (481-500 ms) - on two consecutive occasions per protocol assessments or investigator's judgement	
1 st occurrence	Interrupt treatment with BGB324: i) if QTcF reduces to $\leq$ Grade 1 by 14 days from initial recording, restart BGB324 at a reduced dose of 100mg or discontinue if no further dose reduction is possible. ii) if QTcF does not reduce to $\leq$ Grade 1 by 14 days from initial recording, discontinue BGB324 permanently.
$\geq$ 2 nd occurrence (following a previous dose reduction for QTcF)	Discontinue BGB324 permanently.
$\geq$ Grade 3 ( $\geq$ 501 ms)	
1 st occurrence	Interrupt treatment with BGB324: - if QTcF reduces to $\leq$ Grade 1 by 14 days from initial recording, restart BGB324 at a reduced dose of 100mg or discontinue treatment if dose reduction is not possible - if QTcF does not reduce to $\leq$ Grade 1, discontinue BGB324 permanently.
2 nd occurrence	Discontinue BGB324 permanently
Ventricular arrhythmia	
1 st occurrence	Discontinue BGB324 permanently
Notes:	
• Serum calcium, magnesium and potassium should be measured regularly whilst receiving BGB324; all abnormal results should be corrected	
• The mean QTcF value from triplicate ECG readings should be used when considering dose modification	

QTcF	Recommended BGB324 Dose Modification
	

• Treatment interruption for BGB324-related toxicity should be limited to 14 days

• Dose reduction below 100 mg daily is not possible (a single capsule contains 100 mg BGB324)

• Patients being considered for dose reduction or permanent discontinuation of BGB324 may be discussed with the Medical Monitor

• Patients require an ECG twice weekly for the first 2 weeks after recommencing BGB324 following an interruption (see Section 5.3.9)

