**ECIs for this trial include:**

- an overdose of Sponsor's product (either pembrolizumab or BGB324), as defined in [Section 7.8](#), that is not associated with clinical symptoms or abnormal laboratory results.
- an elevated AST or ALT lab value that is greater than or equal to 3X the upper limit of normal and an elevated total bilirubin lab value that is greater than or equal to 2X the upper limit of normal and, at the same time, an alkaline phosphatase lab value that is less than 2X the upper limit of normal, as determined by way of protocol-specified laboratory testing or unscheduled laboratory testing\*

\*Note: These criteria are based upon available regulatory guidance documents. The purpose of the criteria is to specify a threshold of abnormal hepatic tests that may require an additional evaluation for an underlying etiology. The trial site guidance for assessment and follow up of these criteria can be found in the Guidance for Potential Drug-Induced Liver Injury (DILI) Cases Meeting Hy's Law Criteria held in the Investigator Trial File Binder (or equivalent).

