## 7.8 Definition of Misuse and Overdose

BGB324 overdose is defined as any dose level administered which exceeds the assigned study dose level (including dose reductions).

For this trial, a pembrolizumab overdose will be defined as  $\geq 1000$  mg (5 times the dose) of pembrolizumab. No specific information is available on the treatment of overdose of pembrolizumab. In the event of overdose, the subject should be observed closely for signs of toxicity. Appropriate supportive treatment should be provided if clinically indicated.

If the pharmacy discovers that an overdose has or may have been administered, they should contact the Study Investigator immediately. The Study Investigator will determine if the overdose is an Event of Clinical Interest (see [Section 7.4.3.2](#)).

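### Table 12 restarts BGB324 at 200 mg after an intolerable Grade 2 event even for a patient already on 100 mg, doubling that patient's dose if followed as written

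*Protocol*

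**What the plan says.** Table 12 sets the response to BGB324-related toxicity by CTCAE grade. For the first or second occurrence of the same intolerable Grade 2 event, the site interrupts BGB324 until recovery and then follows the instruction "Resume dosing at 200 mg". No condition on the patient's current dose is attached. Occurrences are counted per event, so a new kind of event is a first occurrence even in a patient who has already been reduced.

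The Grade 3 row of the same table does provide for an earlier reduction: "Discontinue permanently if dose has already been reduced". Table 13, for QTcF prolongation, does so too: "restart BGB324 at a reduced dose of 100mg or discontinue if no further dose reduction is possible".

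Section 6.6.1 adds: "Only one dose reduction from 200 mg to 100 mg daily dose is possible". Section 7.8 states: "BGB324 overdose is defined as any dose level administered which exceeds the assigned study dose level (including dose reductions"). Section 7.4.3.2 lists among the events of clinical interest "an overdose of Sponsor's product (either pembrolizumab or BGB324") where there are no clinical symptoms or abnormal laboratory results, and requires these events to be reported to the sponsor within 24 hours.

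**The concern.** The row names a specific restart dose as though every patient were on 200 mg. The protocol itself creates a group who are not: patients reduced for an earlier event, and patients who would start at dose level -1 if the Data Review Committee recommended it. For them the printed instruction is an increase in dose immediately after a toxicity bad enough to stop treatment.

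The clearest case is a patient reduced to 100 mg for QTcF prolongation under Table 13 who later has a first intolerable Grade 2 event of another kind. Table 12 sends this patient back to the dose at which QTcF was prolonged. Section 6.6.2 says "Treatment with BGB324 produces QTc prolongation", and the monkey cardiovascular study in Section 1.3.2 reports: "Dose-dependent increase in QTc interval was noted at all dose levels". A further QTcF episode after a reduction for QTcF leads to permanent discontinuation under Table 13, so the patient could lose BGB324 altogether because of the restart.

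**Working it through.** No sample size, power or error rate is involved. The check is whether the text leads a patient on 100 mg to a 200 mg restart, and whether any other text prevents it.

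**1. Can a patient be on 100 mg when the row applies?** Yes, by several routes:

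| Route to 100 mg daily | Source |
|---|---|
| First Grade 3 event, or third occurrence of an intolerable Grade 2 event | Table 12 |
| QTcF prolongation, Grade 2 (on two consecutive occasions or by investigator judgement) or Grade 3 and above, recovering within 14 days | Table 13 |
| Diarrhea, rash or renal toxicity that resolves after BGB324 is withheld | Tables 15, 16, 17 |
| Start at dose level -1 (200 mg on Days 1 to 3, then 100 mg) | Sections 4.1, 8.2.1 |

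**2. What does each relevant row provide for a patient already on 100 mg?**

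| Row | Provision for 100 mg |
|---|---|
| Table 12, Grade 1 or tolerable Grade 2 | None; refers to keeping 200 mg |
| Table 12, intolerable Grade 2, 1st or 2nd occurrence | None; restart at 200 mg |
| Table 12, intolerable Grade 2, 3rd occurrence | None; reduce to 100 mg, which is no change |
| Table 12, Grade 3, 1st occurrence | Yes; discontinue |
| Table 13, first QTcF occurrence | Yes; discontinue |

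Of the three rows with a gap, the 1st/2nd-occurrence row is the one that fixes a dose at restart. The first row is not naturally an order to increase, and the third-occurrence row merely leaves no action.

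**3. Size of the step.** Restart dose in the row divided by dose before interruption = 200 mg / 100 mg = 2.0.

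**4. Does any other text in Section 6.6 stop it?** Section 6.6.1 and the notes to Table 12 limit how far the dose can go down. They do not forbid going back up or say to resume the earlier dose. The note on the Medical Monitor concerns patients being considered for reduction or permanent discontinuation, and even then consultation is optional; a restart at 200 mg is neither.

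**5. Consistency with Section 7.8.** If the assigned dose is 100 mg after a reduction, 200 mg exceeds it and meets the overdose definition. The instruction in Table 12 and the ceiling in Section 7.8 cannot both be followed for that patient.

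**6. How many patients?** This cannot be calculated. The row is reached only by a patient on 100 mg who has a first or second intolerable Grade 2 BGB324-related event that leads to interruption and recovers within 14 days. QTc prolongation, diarrhea, rash and renal toxicity have their own tables. The protocol gives no rate for the remaining events among patients on 100 mg.

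**The case against.** The strongest reply is that the doubling comes from an unnatural reading. To resume suggests going back to what was being taken, and Table 12 reads as though written for a patient at the standard dose. The visit schedule in Section 5.1.1 likewise lists 200 mg of BGB324 for Cycles 2 to 35 without exceptions, and nobody would take that as raising reduced patients. The single permitted reduction, and the permanent discontinuation in Table 13 after a second QTcF episode, imply a one-way step. On this view Section 7.8 shows that re-escalation is an error; alternatively, if Table 12 validly reassigns the patient to 200 mg, there is no overdose at all.

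There are also safeguards. The column is headed as a recommendation, and ECGs are required twice weekly for two weeks after an interruption. In the monkey study the QTc change was generally below 10% at the two lower doses named (7.5 and 15 mg/kg). The dose level -1 route exists only if the committee chooses that level.

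Much of this stands as a prediction of behaviour: a careful investigator would probably resume 100 mg. The reporting consequence should also be put cautiously, because Section 7.8 leaves it to the investigator to decide whether an overdose is an event of clinical interest. It does not rescue the row. The row names a dose rather than saying to resume the previous one, and the authors wrote in an earlier reduction where they had it in mind, in the Grade 3 row and in Table 13. That other sections imply a lasting reduction confirms that the row is out of line with the rest of the protocol. ECGs after restart can detect QTc prolongation but do not prevent it. Dosing across up to about 20 sites should not depend on staff overriding the printed instruction.

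**Conclusion.** The point holds. As written, Table 12 gives the wrong restart dose for a patient already on 100 mg: a twofold daily dose after a new intolerable toxicity, in conflict with Section 7.8. This assumes that the row is applied literally and that a reduction, or a start at dose level -1, sets the assigned dose at 100 mg. How often it would arise is unknown and may be low. No effect is claimed on error rates, endpoints or the committee's counts of dose reductions. It should be corrected on patient-safety grounds; the lesser gaps in the two neighbouring rows are best closed in the same edit.

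**What to change.** Amend three rows of Table 12, with the sponsor's clinicians confirming the wording:

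- **Intolerable Grade 2, 1st or 2nd occurrence:** resume at the dose taken before the interruption (200 mg, or 100 mg if already reduced or started at dose level -1); no re-escalation.
- **Grade 1 and tolerable Grade 2:** maintain the current dose.
- **Intolerable Grade 2, 3rd occurrence:** reduce to 100 mg, or discontinue permanently if already at 100 mg, in line with the Grade 3 row.

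The first change is the essential one. The third is a clinical choice that the sponsor may prefer to settle differently, but some action needs to be stated. The cost is the wording of three rows in one protocol table, with no effect on sample size, endpoints or schedule.
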